2. INTRODUCTION

2.1. Background

Lichen planus is an inflammatory skin condition characterized by purple, polygonal, pruritic papules, and plaques. The lesions are often covered by lacy, reticular, white lines known as Wickham striae. Lichen planus can affect any ectodermally derived tissues, including the skin (most commonly), nails, and mucous membranes. Onset is usually acute, affecting the flexor surfaces of the wrists, forearms, and legs. Oral LP can be the sole clinical presentation of the disease or accompanied by cutaneous or other mucosal manifestations, including the genital area, gastrointestinal tract, and eyes. Classic cases of LP may be diagnosed clinically, but a biopsy is often helpful and is required for more atypical cases ([Usatine and Tinitigan 2011](#)). Itch is present in most patients and is considered the most bothersome symptoms of LP ([Welz-Kubiak and Reich 2013](#)). Lichen planus is associated with relatively high rates of depression and anxiety. A recent meta-analysis showed a high prevalence of signs of depression (27%) and anxiety (28%) in patients with LP ([Jalenques et al 2020](#)).

The prevalence of LP is 0.89% in the general population and 0.98% in patients seeking dermatological care, according to a recent meta-analysis of 46 studies ([Li et al 2020](#)). The prevalence of cutaneous LP is reported to range between 0.2% and 1.0% of the adult population, and it is outnumbered by oral LP in most study populations ([Boyd and Neldner 1991](#), [Le Cleach and Chosidow 2012](#)). Patients with LP are usually between the ages of 30 and 60 years, and there appears to be a slightly higher prevalence in women (60%; [Axell and Rundquist 1987](#)). While oral LP affects females more frequently than males ([Axell and Rundquist 1987](#), [Li et al 2020](#)), cutaneous LP does not demonstrate a prominent sex predilection ([Irvine et al 1991](#)). Cutaneous LP tends to manifest during the fifth and sixth decades of life, with almost two-thirds of patients presenting with the disease between the ages of 30 and 60 years ([Schwager et al 2019](#), [Wagner et al 2013](#)). The majority of cutaneous LP lesions resolve spontaneously over 1 to 2 years, often with a residual hyperpigmented macule ([Weston and Payette 2015](#)).

Lichen planus is a T cell-mediated disease affecting the stratified squamous epithelia of the skin and/or mucous membrane. Histologically, the disease is characterized by a lichenoid inflammatory infiltrate and vacuolar degeneration of the basal layer of the epidermis. Several alterations in the expression of cytokines and chemokines in lesions or serum of patients with LP have been described. Serum levels of IL-5, IL-6, IL-8, IL-9, IL-10, IL-12, IL-17, IL-22, tumor necrosis factor α , transforming growth factor β , IFN- γ , CXCR-3, CXCR-4, CXCL-10, CXCL-12, CCR1, CCR3, CCR4, CCL5-CCR5, and CCL17-CCR4 have been found to be elevated ([Chen et al 2013](#), [Kurago 2016](#), [Weber et al 2017](#), [Zychowska et al 2020](#)). Recent studies demonstrated that the inflammation in cutaneous LP is dominated by IFN- γ , IL-6, and IL-21 and the proinflammatory milieu is dominated by STAT1 activation ([Boch et al 2021](#), [Shao et al 2019](#)). All of these cytokines, IL-21, IFN- γ , IL-6, and Type I IFN, use JAK1 for signal transduction. Of note, JAK1 has been reported to be overexpressed in dermal skin of LP ([Alves de Medeiros et al 2016](#)). Therefore, JAK1 blockade could be beneficial for cutaneous LP.

Patients with LP currently have limited treatment options, which include irritant avoidance and first-line treatment with topical corticosteroids. Topical calcineurin inhibitors are the second line of choice when topical corticosteroids are not effective or not tolerated.

Ruxolitinib is a small molecule inhibitor of the JAKs, which play an important role in signal transduction following cytokine and growth factor binding to their receptors. Increased production of cytokines and growth factors has been associated with a number of chronic inflammatory conditions, including AD, vitiligo, and other autoimmune diseases of the skin. Therefore, JAK inhibition may be expected to be efficacious in these diseases (refer to the [IB](#) for more information).

The efficacy of ruxolitinib cream, a JAK1/2 inhibitor, has been demonstrated in inflammatory dermatoses such as AD and vitiligo. Ruxolitinib cream has shown statistically significant and clinically meaningful efficacy in 2 pivotal Phase 3 studies (INCB 18424-303 and -304) in participants with mild to moderate AD and 3% to 20% affected BSA (excluding the scalp; [Papp et al 2020](#)). In both AD Phase 3 studies, more than 50% (53.8% and 51.3%) of participants (≥ 12 years of age) who applied ruxolitinib 1.5% cream BID for 8 weeks achieved an IGA-TS (ie, IGA score of 0 or 1 with ≥ 2 -grade improvement from baseline) compared with 15.1% and 7.9% of participants who applied vehicle cream, respectively. Participants who applied ruxolitinib cream also saw a substantial improvement in itch compared with participants who applied vehicle cream in both studies (50.7% and 52.2% for ruxolitinib cream vs 16.3% and 15.4% for vehicle cream, respectively). In addition, ruxolitinib 1.5% cream administered BID was safe and well-tolerated in adolescent and adult participants with AD. Ruxolitinib 1.5% cream is approved in the US as Opzelura™ for the topical short-term and noncontinuous chronic treatment of mild to moderate AD in nonimmunocompromised patients 12 years of age and older whose disease is not adequately controlled with topical prescription therapies or when those therapies are not advisable.

Ruxolitinib 1.5% cream has demonstrated efficacy in vitiligo. Studies INCB 18424-306 and -307 were identically designed randomized, VC, Phase 3 studies in adolescent and adult participants (≥ 12 years old, $\approx 10\%$ of whom were adolescents) with vitiligo. Participants received blinded study treatment for 24 weeks and were then offered the opportunity to receive an additional 28 weeks of treatment with ruxolitinib 1.5% cream BID. Both studies met the primary endpoint ($p < 0.0001$ for both studies), demonstrating that significantly more participants treated with ruxolitinib 1.5% cream BID achieved a $\geq 75\%$ improvement from baseline in the Face Vitiligo Area Scoring Index at Week 24 compared to participants treated with a vehicle control. In addition, ruxolitinib 1.5% cream was safe and well-tolerated in both adolescents and adults with vitiligo.

Recently, the potential benefit of ruxolitinib 1.5% cream BID was reported in a single-arm, open-label study in participants with cutaneous LP treated for 8 weeks ([Mangold et al 2021](#)). Twelve patients with a median age of 63 years (range: 34-81 years) participated in the study. At Week 4 (primary endpoint), total body lesion number decreased by a median of 50 lesions (interquartile range: 25-723; $p < 0.001$). Mean (STD) mCAILS scores decreased by 11.0 (6.2) in index treatment lesions and 3.4 (5.6) in index controls, for a mean difference of 7.6 (8.8; $p = 0.016$). Ten of 12 index treatment lesions (83.3%) achieved treatment response, as defined by $\geq 50\%$ reduction in mCAILS score, compared to 4 of 12 controls (33.3%; $p = 0.077$). Post hoc analysis, which excluded 4 participants who unintentionally treated their control lesions at any point during the study, revealed response of 7 of 8 treatment lesions (87.5%) compared to 1 of 8 control lesions (12.5%; $p = 0.04$). All participants were responsive ($\geq 50\%$ improvement) based on Patient Global Assessment score at Week 4; 2 of 12 were 100% clear, 5 of 12 had $\geq 90\%$ improvement, 4 of 12 had marked ($\geq 75\%$ to 90%) improvement, and 1 of 12 had

moderate ($\geq 50\%$ to 75%) improvement. A significant reduction ($p = 0.006$) in mean pruritus NRS scores was reported at Week 4. Only 1 AE was deemed to be possibly related to the study treatment ("abnormal taste" reported at Week 1) and was classified as mild. All other AEs were judged as mild to moderate and were determined to be unrelated to the study medication.

This study is designed to evaluate the efficacy and safety of ruxolitinib 1.5% cream in participants with cutaneous LP.

2.1.1. Scientific Rationale for Study Design

Similar to AD and vitiligo, LP is considered to be an inflammatory dermatosis. The pathogenesis of LP involves autoimmunity and several cytokines that are dependent on the JAK-STAT pathway for signal transduction. Similar to AD and vitiligo, JAK1- and JAK2-associated cytokines are involved in the pathogenesis of cutaneous LP. Prior studies have shown overexpression of IFN- γ , IL-21, IL-4, IL-12A, and tumor necrosis factor in LP ([Pietschke et al 2021](#), [Shao et al 2019](#)). Ruxolitinib is a selective inhibitor of JAK1 and JAK2, and based on its demonstrated efficacy in both AD and vitiligo in well-designed pivotal Phase 3 trials (INCB 18424-303/-304 and INCB 18424-306/-307) and data from [Mangold et al \(2021\)](#), ruxolitinib 1.5% cream is expected to have potential activity in cutaneous LP.

While the study by [Mangold et al \(2021\)](#) provides preliminary evidence of the efficacy of ruxolitinib 1.5% cream in patients with LP, this was a single-arm study with a small sample size, and these findings need to be replicated in a larger randomized controlled trial as a proof of concept. Lichen planus lesions mostly resolve spontaneously over a period of 1 to 2 years, and the aim of treatment is to hasten recovery and reduce associated symptoms such as itching. Given the high rate of spontaneous resolution, it is important to demonstrate the efficacy of ruxolitinib 1.5% cream against a VC arm. Although ruxolitinib 1.5% cream has been demonstrated to improve AD at 8 weeks, LP lesions involve significantly more skin changes. [Mangold et al \(2021\)](#) demonstrated reduction in lesion count by 50% after 4 weeks of open-label treatment with ruxolitinib 1.5% cream. However, concern with spontaneous resolution of LP remains. In the study by [Mangold et al \(2021\)](#), approximately 33% of control lesions achieved treatment response, as defined by $\geq 50\%$ reduction in mCAILS score at Week 4. Based on these findings, it is crucial to demonstrate the efficacy of ruxolitinib 1.5% cream in participants with cutaneous LP as a proof-of-concept Phase 2 study with a longer treatment period (16 weeks was chosen for this study) before moving to confirmatory Phase 3 studies. In addition, there is a need to demonstrate the long-term safety and efficacy of ruxolitinib 1.5% cream in LP by including an OLE period.

This study will evaluate the efficacy and safety of ruxolitinib 1.5% cream BID versus vehicle in participants with LP. The VC period is 16 weeks. Participants who are randomly assigned to ruxolitinib 1.5% cream will continue to treat active LP areas during the OLE period for an additional 16 weeks. Participants assigned to vehicle initially will then be crossed over to receive active treatment for an additional 16 weeks. This design will provide a well-controlled assessment of the efficacy of ruxolitinib 1.5% cream in participants with LP compared to vehicle.

2.1.2. Justification for Dose

The ruxolitinib cream strength and application frequency for this study (ruxolitinib 1.5% cream BID) was selected primarily based on preliminary evidence from the open-label study by Mangold et al (2021) and data from the Phase 3 pivotal studies (INCB 18424-303 and -304) in participants \geq 12 years of age with AD, which evaluated the safety and efficacy of ruxolitinib 1.5% cream BID and ruxolitinib 0.75% cream. Overall, ruxolitinib 1.5% cream was found to be more efficacious than ruxolitinib 0.75% cream, while the safety and tolerability profiles of both treatment arms were comparable and nondifferentiating. Of note, the Phase 3 efficacy and safety findings were on par and thus fully confirmatory of the outcomes of the earlier Phase 2 (INCB 18424-206) dose range-finding study. Similarly, Phase 3 pivotal studies in vitiligo (INCB 18424-306 and -307) provide further support for the superior efficacy of ruxolitinib 1.5% cream versus vehicle cream.

Given the known data and the pathogenic and clinical manifestations of LP, ruxolitinib 1.5% cream BID was selected as the treatment regimen for this study.

2.2. Benefit/Risk Assessment

Ruxolitinib 1.5% cream showed statistically significant and clinically meaningful improvement in the signs and symptoms of AD in participants with mild to moderate AD, including itch (Papp et al 2020). Given that LP has an itch component to the disease, it is likely that participants with LP will benefit from ruxolitinib cream in treating itch.

Safety data from the Phase 3 AD studies (INCB 18424-303 and -304) demonstrated that ruxolitinib 1.5% cream BID applied continuously for 8 weeks followed by prolonged (44 weeks) intermittent use is safe and well-tolerated. The TEAEs were generally Grade 1 or 2 in severity and were most often events of nasopharyngitis and upper respiratory tract infection. Frequencies of these events were within the expected range for the general AD population.

Safety and tolerability in the Phase 2 and Phase 3 studies in vitiligo (INCB 18424-211, -306, and -307) showed that the rate of Grade 3 TEAEs, SAEs, and TEAEs leading to discontinuation was low. There were no significant TEAEs or application site events and no clinically relevant hematological changes suggestive of systemic toxicity.

In the study by Mangold et al (2021), all AEs were mild to moderate in severity and, with 1 exception, all were unrelated to the study medication. This provides some evidence of the safety of ruxolitinib 1.5% cream in participants with LP.

Results from dermal safety studies in healthy adult participants (INCB 18424-104, -105, -106, -107, and -108) to evaluate local tolerability demonstrated that ruxolitinib 1.5% cream did not cause sensitization and was only slightly irritating under exaggerated testing conditions (occlusive application). In addition, ruxolitinib 1.5% cream was not phototoxic and did not induce photosensitization. This was further confirmed by the Phase 3 (INCB 18424-303 and -304) safety data, where ruxolitinib 1.5% cream BID was well-tolerated at the application sites with infrequently reported application site reactions. The most frequently reported application site reaction events were application site pain (lowest-level terms were primarily application site burning or application site stinging) and application site pruritus. Each of these events occurred in a lower proportion of participants in the ruxolitinib 1.5% cream BID treatment group (< 1%) compared with the vehicle cream treatment group (3%-5%) during the 8-week VC period, which

may be attributable to worsening of the underlying disease in the absence of active drug treatment. More detailed information about the known and expected benefits and risks and reasonably expected AEs of ruxolitinib cream may be found in the [IB](#).

The efficacy and safety data from AD and vitiligo studies as well as data from the study by Mangold et al ([2021](#)) in cutaneous LP provide support of the expected positive benefit-risk ratio of ruxolitinib cream in LP. Furthermore, given that LP has an itch component to the disease, it is anticipated that participants with LP will benefit from ruxolitinib cream in treating itch.

3. OBJECTIVES AND ENDPOINTS

[Table 4](#) presents the objectives and endpoints.

Table 4: Objectives and Endpoints

Objectives	Endpoints
Primary	
To establish the efficacy of ruxolitinib 1.5% cream BID in participants with cutaneous LP.	IGA-TS response (defined as an IGA score of 0 or 1 with \geq 2-grade improvement from baseline) at Week 16. [Proportion of participants achieving IGA-TS at Week 16]
Secondary	
To further assess the treatment effects of ruxolitinib 1.5% cream BID in participants with cutaneous LP.	
IGA-TS response at each scheduled postbaseline visit up to and including Week 32. [Proportion of participants achieving IGA-TS at each scheduled postbaseline visit]ITCH4 response (defined as a \geq 4-point improvement in Itch NRS score from baseline) at each scheduled postbaseline visit up to and including Week 32. [Proportion of participants with ITCH4 at each scheduled post-baseline visit]Time to achieve ITCH4.Change from baseline in the Skin Pain NRS score at each scheduled postbaseline visit up to and including Week 32.
To evaluate the safety and tolerability of ruxolitinib 1.5% cream BID.	The type, frequency, and severity of AEs, including changes in vital signs and clinical laboratory blood samples.

Table 4: Objectives and Endpoints (Continued)

Objectives	Endpoints

4. STUDY DESIGN

4.1. Overall Design

This is a Phase 2, randomized, DBVC study in participants at least 18 years of age who have predominantly cutaneous LP (covering $\leq 20\%$ BSA) and baseline IGA score ≥ 3 . The study will consist of a 16-week DBVC period followed by a 16-week OLE period. Participants who were initially assigned to ruxolitinib 1.5% cream will continue with active treatment during the OLE period, while those participants who were initially assigned to vehicle will cross over to active treatment.

Approximately 60 participants will be randomized 1:1 to either ruxolitinib 1.5% cream or vehicle cream (see [Figure 1](#)). Participants will be stratified by baseline IGA score (3 or 4). Participants will apply either ruxolitinib 1.5% cream or vehicle cream (both BID) through Week 16 to all affected areas identified at baseline. At Week 16, participants who meet the criteria (compliant with the Protocol and without safety concerns) will enter the 16-week OLE period. Participants randomized to vehicle in the VC period will be crossed over to ruxolitinib 1.5% cream, and participants randomized to ruxolitinib 1.5% cream at baseline will continue to apply ruxolitinib cream through Week 32. In the OLE period, participants will only treat lesions that are symptomatic. At Week 16, the LP treatment area will be evaluated by the investigator to assess the disease and confirm whether treatment continuation is required (IGA score ≥ 1) during the OLE period or can otherwise (re)enter an observation/no treatment cycle (IGA score = 0; see also [Section 6.1](#)). Treatment assignment during the DBVC period will remain blinded until all participants have completed treatment or discontinued. [Table 3](#) presents the SoA.

The COVID-19 global pandemic may present challenges to the normal conduct of this study (including AE and laboratory assessments), requiring the implementation of potential mitigation strategies described in [Appendix B](#).

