Study Design	This is a 16-week, randomized, DBVC study with a 16-week OLE period with a crossover to active treatment for participants who complete the 16-week DBVC period (vehicle cream), followed by a 30-day post-treatment, safety follow-up visit. Participants initially randomized to the active treatment arm will continue with ruxolitinib 1.5% cream during the OLE period.
Estimated Duration of Study Participation	Estimated total duration of participants is up to approximately 40 weeks, including up to 4 weeks for screening, up to 32 weeks for treatment, and 30 days for safety follow-up.
Data Safety Monitoring Board/Data Monitoring Committee	No

Treatment Groups and Duration:

This is a Phase 2, randomized, DBVC study with a DBVC period of 16 weeks followed by an OLE period of 16 weeks. Participants who were initially assigned to ruxolitinib 1.5% cream will continue with active treatment during the OLE period, while those participants who were initially assigned to vehicle will cross over to active treatment.

Approximately 60 participants will be randomized 1:1 to either ruxolitinib 1.5% cream or vehicle cream (see [Figure 1](#)). Participants will be stratified by baseline IGA score (3 or 4). Participants will apply either ruxolitinib 1.5% cream or vehicle cream (both BID) through Week 16 to all affected areas identified at baseline. At Week 16, participants who meet the criteria (compliant with the Protocol and without safety concerns) will enter the 16-week OLE period. Participants randomized to vehicle in the VC period will be crossed over to ruxolitinib 1.5% cream, and participants randomized to ruxolitinib 1.5% cream at baseline will continue to apply ruxolitinib cream through Week 32. In the OLE period, participants will only treat active lesions. At Week 16, the LP treatment area will be evaluated by the investigator to assess the disease and confirm whether treatment continuation is required (IGA score \geq 1) during the OLE period or can otherwise (re)enter an observation/no treatment cycle (IGA score = 0). Treatment assignment during the DBVC period will remain blinded until all participants have completed treatment or discontinued.

[Table 3](#) presents the SoA. Adherence to the study design requirements, including those specified in the SoA, is essential and required for study conduct.

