6. STUDY TREATMENT

6.1. Study Treatments Administered

Ruxolitinib cream or matching vehicle will be applied as a thin film BID, with applications approximately 8 to 12 hours apart in the morning and in the evening at least 1 hour before bedtime.

At the baseline visit, an estimate of the %BSA to be treated will be used by the IRT system to calculate the number of tubes of study cream to be dispensed. During clinic visits, the participant should apply a thin film of study cream in front of site staff until all the affected areas to be treated are covered. This supervised application will be limited to 1 application of the study drug during the clinic visit. All areas identified at baseline should continue to be treated through the end of the DBVC period (Week 16) unless the participant meets criteria for stopping study cream. If there are new areas to be treated, including expansion of existing areas or development of new areas, after consultation with the investigator, study cream should be applied to these areas in addition to the areas treated at baseline (total affected areas \leq 20% BSA), and the percentage of BSA to be treated will be recalculated and increased. This new estimate will be entered into the IRT system to calculate the number of tubes of study cream to be dispensed. Participants whose new areas to be treated in addition to the areas identified at the baseline visit exceed 20% BSA should be discontinued from study treatment and the EOT assessment should be completed.

During the OLE period, starting at the Week 16 visit, the LP treatment areas will be evaluated by the investigator to assess if they still have disease and confirm whether the participant requires continuation of therapy (IGA score \geq 1) or can otherwise (re)enter the observation/no treatment cycle (IGA score = 0). Participants will stop treatment applications 3 days after all LP signs and symptoms have resolved. Multiple cycles of treatment/no treatment may be utilized as needed and treatment start/stop dates should be recorded by the participant in their eDiary. At any time during the OLE period, if a participant's new areas to be treated in addition to the areas identified at the previous visit exceed 20% BSA, then the participant should be discontinued from study treatment and the EOT assessment should be completed.

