8.2.2. Investigator's Global Assessment

The IGA to assess cutaneous LP has been modified by the sponsor to appropriately assess LP. The investigator/rater will assess the lesions at the study visits indicated in [Table 3](#) by using the descriptors [REDACTED] that best describe the overall appearance of the lesions at a given timepoint. It is not necessary that all characteristics under the morphological description be present.

IGA-TS is defined as an IGA score of 0 or 1 with \geq 2-grade improvement from baseline.

A high-contrast, black and white image showing a series of horizontal bars. The bars are mostly black, with white spaces between them. The bars are of varying lengths and are set against a white background. The image is heavily processed, appearing as a binary black and white pattern.

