8.2.8. Patient-Reported Outcomes

Patient-reported outcomes will be collected and assessed as outlined in the SoA (see [Table 3](#)). For all patient-reported outcome assessments conducted at the study site, in order to avoid bias in the participants' responses to the questionnaires, assessments should be completed before any other evaluations or study procedures on the day of the study visit and prior to treatment-related discussions with the investigator or study site staff.

8.2.8.1. eDiary Assessments

The participant will be instructed to complete and record their Itch NRS and Skin Pain NRS scores via eDiary every evening beginning on the day of screening through Week 32 or ET.

Both the Itch NRS and Skin Pain NRS are a daily participant-reported measure (24-hour recall) of the worst level of itch or skin pain intensity related to LP.

The participants will rate the following:

- Itch NRS: Itch severity of their LP by selecting a number from 0 (no itch) to 10 (worst imaginable itch) that best describes their worst level of itching in the past 24 hours.
- Skin Pain NRS: Pain severity of their LP by selecting a number from 0 (no pain) to 10 (worst imaginable pain) that best describes their worst level of pain in the past 24 hours.

The average of the 7-day Itch NRS score prior to the baseline visit (minimum 4 out of 7 days' data required) will be used to determine if a participant meets the inclusion criteria.

Detailed directions for the administration of the eDiary will be provided in the Study Manual.

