3. STUDY DESIGN

[figure not shown]
This is a Phase 2, randomized, DBVC study in participants aged ≥ 18 years who have predominantly cutaneous LP (covering $\leq 20\%$ BSA) and baseline IGA score ≥ 3 . The study will consist of a 16-week DBVC period followed by a 16-week OLE period.

Approximately 60 participants will be randomized 1:1 to either ruxolitinib 1.5% cream BID or vehicle cream BID. Participants will be stratified by baseline IGA score (3 or 4). Participants will apply either ruxolitinib 1.5% cream BID or vehicle cream BID through Week 16 to all affected areas identified at baseline.

At Week 16, participants who meet the criteria (compliant with the Protocol and without safety concerns) will enter the 16-week OLE period. Participants randomized initially to vehicle cream in the DBVC period will be crossed over to ruxolitinib 1.5% cream BID and participants randomized to ruxolitinib 1.5% cream at baseline will continue to apply ruxolitinib 1.5% cream BID through Week 32. In the OLE period, participants will only treat active lesions up to 20% BSA. At Week 16, the LP treatment area will be evaluated by the investigator to assess the disease and confirm whether treatment continuation is required (IGA score ≥ 1) during the OLE period or can otherwise (re)enter an observation/no treatment cycle (IGA score = 0).

The study schema is shown below in [Figure 1](#).

Figure 1: Study Design Schema

The primary analysis will occur after the primary database lock, when all participants have completed the DBVC period. The final analysis will occur when all participants have completed or withdrawn from the study.

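### Does Protocol Section 4.1's limit of open-label treatment to symptomatic lesions set up a regimen that conflicts with Section 6.1?

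*Protocol*

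**What the plan says.** Three parallel descriptions of the open-label extension (OLE) use two different words.

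- Protocol Section 4.1: "In the OLE period, participants will only treat lesions that are symptomatic".
- Protocol Section 1 (Protocol Summary): "In the OLE period, participants will only treat active lesions".
- SAP Section 3: "In the OLE period, participants will only treat active lesions up to 20% BSA".

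Protocol Section 6.1 gives the dosing instructions. From Week 16 the investigator looks for remaining disease to "confirm whether the participant requires continuation of therapy". An IGA of 1 or more means continuation, and an IGA of 0 means an observation cycle. On stopping, it says: "Participants will stop treatment applications 3 days after all LP signs and symptoms have resolved". It also allows repeated cycles on and off treatment.

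Under Section 8.2.2 the IGA uses the descriptors "that best describe the overall appearance of the lesions at a given timepoint". Itch and skin pain are recorded separately, each as one daily diary score per participant (Section 8.2.8.1).

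**The concern.** The protocol tends to keep symptoms apart from visible disease. Section 2.1.1 says "the aim of treatment is to hasten recovery and reduce associated symptoms such as itching", which names recovery and symptoms as two things, and the stopping rule in Section 6.1 lists signs as well as symptoms. On that usage a symptomatic lesion is one that itches or hurts, whereas the IGA follows what can be seen.

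Take a participant in the OLE whose remaining lesions are all visible (IGA of at least 1) but cause no itch or pain. The Section 4.1 sentence leaves nothing to treat. Section 6.1 keeps the participant on therapy, because signs remain. If some sites followed one text and some the other, OLE cream exposure (SAP Section 6.4) and the IGA-TS rates after Week 16 would mix two regimens. IGA-TS up to Week 32 is a listed secondary endpoint, so the point deserved a check.

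**Working it through.** The plan gives no figure on this point to reproduce. The check sets the passages side by side and then traces which outputs could be affected.

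**1. What each passage makes treatment depend on**

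| Place | Criterion |
|---|---|
| Protocol 1 (Summary) | active lesions; continue at IGA of at least 1 |
| Protocol 2.1.1 | active areas |
| Protocol 4.1, sentence at issue | symptomatic lesions |
| Protocol 4.1, later in the same paragraph | continue at IGA of at least 1, observe at 0, with a reference to 6.1 |
| Protocol 6.1 | disease still present; continue at IGA of at least 1; stop 3 days after signs and symptoms are gone |
| Protocol 6.1, Table 5 | affected areas, as needed |
| Protocol 6.5 | interruption on clearance of the disease |
| SAP 3 | active lesions; continue at IGA of at least 1 |

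Only one entry speaks of symptomatic lesions. Section 4.1 itself carries the IGA threshold used in Section 6.1, so following 4.1 and following 6.1 are not two separate policies. What is left is one sentence that, on one reading, does not fit the rest of its own paragraph.

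**2. When the two rules collide**

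The sentence in 4.1 works lesion by lesion, while the stopping rule in 6.1 works at participant level. While any lesion itches or hurts, both can be met. They collide only when every remaining lesion is visible and none itches or hurts, and only if *symptomatic* excludes such lesions. No instrument in the visible text scores itch or pain for single lesions, so the strict reading would need a judgement that the visible procedures do not record.

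**3. Which outputs could move**

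- OLE visits after Week 16 (Protocol Table 3): Weeks 18, 20, 24, 28 and 32, so 5.
- OLE groups (SAP Section 5.2): vehicle to ruxolitinib, and ruxolitinib throughout, so 2.
- Main IGA-TS rates: 5 x 2 = 10, plus OLE cream exposure. The subgroup tables and figures in SAP Appendix A that cover the treatment periods come on top.

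This is a count of outputs, not an effect size.

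**4. Whether IGA-TS would change**

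IGA-TS requires a score of 0 or 1 and an improvement of at least 2 grades. Entry requires a baseline IGA of 3 or 4 (Protocol Section 5.1).

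- Baseline 3, current score 1: 3 - 1 = 2, a response.
- Baseline 4, current score 1: 4 - 1 = 3, a response.

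Every participant at IGA 1 is therefore already a responder. The wording can bear on IGA-TS only at an IGA of 2 or more, or where an IGA of 1 later worsens, and then only in someone with no itching or painful lesion left.

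**5. What cannot move**

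The Week 16 primary endpoint, its test and the sample size all precede the OLE. Time to ITCH4 is confined to the double-blind period (SAP Section 7.4.3). The visible text of SAP Section 7.4.2 specifies no hypothesis test after Week 16.

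**The case for a change.** The strongest case for acting is that the word is restrictive (*only*), that the visible text defines neither *symptomatic* nor *active*, and that the reference to Section 6.1 does not say which text prevails. The test case is also plausible. The protocol expects the cream to relieve itch, and its background section notes that healed lesions often leave pigmentation, so visible change without itch may well occur. There is an operational side too. Section 8.8.1 waives the safety follow-up visit for participants in an observation cycle from Week 28 or earlier until Week 32, and Section 6.4 ties OLE compliance handling to being on a treatment cycle. Someone applying no cream at an IGA of 1 or more fits neither status clearly.

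Part of this stands. The wordings differ, and a literal reader could be left unsure. The step from there to a divided regimen is weak, since a site that reads the whole of Section 4.1 meets the IGA threshold in the next sentence. The lack of a definition also carries little weight, because the IGA descriptors are redacted and the design figure is not shown. The follow-up and compliance point depends on the same strict reading and adds no separate evidence that anyone would be handled differently.

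**Conclusion.** This is a clerical slip: one word in an overview paragraph differs from the parallel text. The passages on OLE treatment (Protocol Sections 1, 2.1.1, 4.1 and 6.1 with Table 5, and SAP Section 3) must be reconciled to one wording as an editorial matter, and which rule they state is the sponsor's clinical decision. No change to the design, endpoints or analysis follows.

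The reach is at most the OLE cream exposure and the descriptive IGA-TS summaries at 5 visits in 2 groups. Application in the OLE already varies by design, through as-needed use and repeated cycles, so these summaries pool different patterns of use under any wording. The size of any shift is not computable: the documents do not say how many participants would have visible lesions free of itch and pain, and only those at an IGA of 2 or more, or worsening later from 1, could affect a rate.

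The conclusion assumes that sites read Section 4.1 as a whole and together with Section 6.1. If many applied the single sentence strictly, the OLE summaries would be harder to interpret, but the Week 16 comparison would be the same.
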